### tDCS Montage:

#### **Active Stimulation:**

### tACS Montage:

**Active Stimulation:** tACS montage is the same montage as above. In the case of running a tACS participant, PO7, P6, P08 and AF7, AF8, P9, O1, P10 amps are the same. Frequency set to 2hz.

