**NCT #: NCT04870710**

**January 2nd, 2022**

Protocol Number:	2019P001016
Title:	Feasibility Electrical Stimulation Study for Visual Hallucinations
Design:	Open Label, Non-randomized, Crossover Design with Baseline, Day 5 and 1 Month follow up visits during which tES (Cathodal tDCS & 2hz tACS) were delivered to the visual cortex from Baseline to Day 5 each day (5 days) twice a day for 20mins. Participants first entered the cathodal tDCS condition first and then after a washout period (~2 weeks) entered the 2hz tACS condition to test the effectiveness and feasibility of stimulating the visual cortex using a novel targeting methodology consisting of a lesion network guided brain target near V5/MT.
Objectives:	
Enrollment:	10 Individuals
Clinical Sites:	Beth Israel Deaconess Medical Center, Boston, MA
Patient Population:	Male or female outpatients 18-50 years of age patient's diagnosis with either schizophrenia, schizoaffective disorder, or psychotic bipolar as defined by DSM-5 or DSM-IV-TR criteria
Primary and Secondary Outcomes:	Primary Outcomes: Steady-State Visual Evoked Potentials (SSVEP); Positive and Negative Syndrome Scale (PANSS); Biological Motion Secondary Outcomes: Global Assessment of Functioning (GAF); Velocity Discrimination; International Affective Picture System (IAPS) Task; Montgomery-Asberg Depression Rating Scale (MADRS)

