	
4. skin sensitivity.
 
5. claustrophobia.
 
6. organic brain syndrome
 
7. intellectual disability or other cognitive dysfunction that could interfere with capacity to engage in study as determine by the PI
 
8. a history of substance or alcohol abuse or dependence (other than nicotine) in the last 6 months or otherwise unable to commit to refraining from alcohol use during the acute period of study participation. The acute period of study participation is defined as during their visit and 24 hours before and after their visit.
 
9. Significant suicidal ideation or those who have enacted suicidal behaviors within 6 months prior to intake will be excluded from study participation and referred for appropriate clinical intervention.
 
10. Serious medical illness or instability requiring hospitalization within the next year.
 
11. Experience with any cardiac event.
 
12. Pregnant women, lactating women, women who are breastfeeding and women of childbearing potential who are not using medically accepted forms of contraception (e.g., IUD, oral contraceptives, barrier devices, condoms and foam, or implanted progesterone rods stabilized for at least 3 months).

Statistical Methodology:	
Within and Between comparisons to statistical detect differences in symptoms, visual tasks and electrophysiology measures before and after treatment conditions (cathodal tDCS and 2hz tACS). To determine the effectiveness and feasibility of targeting the visual cortex with a novel targeting methodology to engage target outcomes

**Statement:** The design, conduct and reporting of this trial shall be conducted in accordance with the protocol, the United States 45 Code of Federal Regulations (CFR) part 46 known as “The Common Rule”, 45 CFR 164.502(d), and 164.514(a)-(c) known as “The Privacy Rule” of the Health Insurance Portability and Accountability Act (HIPAA), and the International Conference on Harmonization (ICH)/Good Clinical Practice (GCP). All Investigators will have documented training in The Collaborative Institutional Training Initiative (CITI Program) in Biomedical Research and GCP.

[figure not shown]

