**Study Rationale:** The visual system is an important site of pathology in patients with schizophrenia, schizoaffective disorder, bipolar disorder, Parkinson’s disease, Lewy body dementia, Charles Bonnet syndrome, and brain lesions experiencing visual hallucinations. Visual symptoms are associated with worse poorer outcome and treatment refractoriness. A recent study identified a causal location in the extrastriate visual cortex with visual hallucinations (VH). Two case studies have found that transcranial electrical stimulation of the occipital cortex improved VH in treatment refractory patients with visual hallucinations. While promising it is unclear whether the symptom reductions resulted from activity changes in the visual cortex or not. Here we aim to answer the question whether high definition transcranial direct current stimulation when optimally targeted to a specific brain region (extrastriate visual cortex) can engage the target and improve behavioral symptoms.

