#### **Screening and Baseline Procedures (approximately 3-4 hours)**

Screening and baseline procedures will be conducted in the Massachusetts Mental Health Center (MMHC)/ Beth Israel Deaconess Boston. The urine toxicology screen and pregnancy test will be completed at MMHC or within Beth Israel Deaconess Boston.

- Eligibility pre-screen will include a telephone pre-screening questionnaire that will assess basic inclusion and exclusion criteria.

- Eligibility screen will include a screening questionnaire that will assess more details related to inclusion and exclusion criteria and will be conducted in-person during the clinical diagnostic session (i.e., the first visit to the laboratory).

- Informed consent will be obtained

- Urine toxicology screen

- Urine pregnancy testing for females of childbearing age

**Subjects will be informed that if they do not pass the urine toxicology screen (other than prescribed medication), they will be withdrawn from the study and will not receive compensation for the initial visit. This will be made clear in the pre-screening questionnaire.**

- tES screening questions for tES participation

- Demographics: Subjects will be asked to provide standard demographic information (age, sex, race/ethnicity, level of education, cohabitation status) using forms employed in previous studies.

- Psychiatric, medical, substance use history and medication review

- Signing a release to allow for access to recent psychiatric records, if confirmation of medications or psychiatric history is necessary

- If subjects have previously had a structural MRI performed through BSNIP2, they will be asked for permission to review these scans for use in neuronavigation.

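### Both conditions stimulate one site, so the trial cannot show that the novel targeting method is what is effective; the synopsis should claim less

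*Protocol*

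**What the plan says.** Two rows of the protocol synopsis make targeting something the trial will evaluate. The Design row says that effectiveness and feasibility are to be tested "using a novel targeting methodology consisting of a lesion network guided brain target near V5/MT". The Statistical Methodology row goes further: "To determine the effectiveness and feasibility of targeting the visual cortex with a novel targeting methodology to engage target outcomes".

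The Study Rationale asks a different question, namely whether well-targeted stimulation "can engage the target and improve behavioral symptoms". The Primary Objective concerns symptoms, electrophysiology and motion perception, and does not mention targeting.

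The trial is an "Open Label, Non-randomized, Crossover Design with Baseline, Day 5 and 1 Month follow up visits", with 10 people and a fixed order: "Participants first entered the cathodal tDCS condition first and then after a washout period (~2 weeks) entered the 2hz tACS condition".

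On placement, the tACS Montage section states that the "tACS montage is the same montage as above". It lists eight scalp positions, says that the currents are unchanged and sets the frequency to 2 Hz. Screening and Baseline Procedures adds: "If subjects have previously had a structural MRI performed through BSNIP2, they will be asked for permission to review these scans for use in neuronavigation".

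Primary Analyses plans within-group differences and the difference between the two treatments, by mixed model or non-parametric methods. Under Primary Endpoint, the outcomes are change from baseline in PANSS total, SSVEP voltage and biological motion score.

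**The concern.** A claim that a targeting method is effective is a claim about where stimulation is applied. To support it, something in the data must differ by site, such as this target against a conventional occipital placement or against another region. Here the two conditions share the montage and differ only in waveform.

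If PANSS, SSVEP or biological motion improves, the improvement is as compatible with many other placements as with the lesion-network target. If tDCS and tACS differ, that difference says nothing about location. A report that followed the Statistical Methodology row could credit the targeting method with an effect that the data cannot attribute to it.

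This is not the same point as the lack of a sham condition. A sham at the same site would help with expectation and the passage of time, but it would still leave this target uncompared with any other.

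**Working it through.** The protocol gives no figure to reproduce here. The check is whether the stated claim can be identified from the planned comparisons.

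**Inputs**
- Conditions: cathodal tDCS, then 2 Hz tACS (synopsis, Design).
- Site: the same montage and currents in both (tACS Montage). Call it site A.
- Other sites, or sham: none described.
- Comparisons: within each condition, and between the two (Primary Analyses).

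**Each comparison against the factor it varies**

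| Planned comparison | Site in first term | Site in second term | What differs |
|---|---|---|---|
| tDCS: after vs before | A | none (baseline) | stimulation together with time and expectation |
| tACS: after vs before | A | none (baseline) | stimulation together with time, expectation and the earlier tDCS period |
| tDCS vs tACS | A | A | waveform together with period |

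**Model form.** Write the expected response on treatment as

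E(Y) = b0 + b1 × waveform + b2 × site.

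Waveform takes two values. Site takes one value, so its column is a multiple of the intercept column and b2 cannot be separated from b0. Degrees of freedom for site = levels − 1 = 1 − 1 = 0. This does not depend on the sample size, the variance or the choice between the mixed model and non-parametric methods. No separate statistical analysis plan could change it, because no data at a second planned site would exist.

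**What can be estimated**
- Feasibility of delivering stimulation at this target.
- Before-after change in SSVEP, PANSS and biological motion in each condition, without a control.
- The tDCS-tACS difference at one site, which is confounded with the fixed order.

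**What cannot be estimated**
- Any benefit of this target over another placement, which is what effectiveness of the targeting method requires.

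**Set against the text.** The Study Rationale question, about engagement and improvement, falls in the first list, though only as uncontrolled change. The effectiveness part of the Statistical Methodology row, and of the Design row if read the same way, falls in the second.

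**The case against.** The strongest reply is that this is a feasibility study and that the Design row can be read as testing stimulation delivered at a lesion-network target, not that target against a rival. On this reading the Primary Objective is silent on targeting, the Study Rationale asks only about engagement and improvement, and SSVEP as a primary endpoint addresses engagement. Much of this stands. Feasibility and uncontrolled engagement remain assessable, and the Study Rationale needs no rewriting. The reply does not rescue the Statistical Methodology row, which makes the effectiveness of targeting by a new method the thing to be determined.

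It is also fair to say that one shared montage is good practice for comparing waveforms, since moving the electrodes between conditions would confound waveform with location. The fault lies in the claim and not in the montage.

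A reader might infer more than the protocol supports:
- *That nothing standardises the target.* The tACS Montage section names scalp positions and holds the currents equal, which is standardisation at scalp level. The tDCS montage appears blank in the extracted text, probably a figure that was not reproduced, so it cannot count as missing.
- *That only participants with an earlier scan can be navigated, so two delivery methods are pooled.* The screening section says that permission will be sought to use such scans. It does not say that navigation moves the electrodes, or that nobody else can be navigated. Study Timeline lists no MRI, which makes the second inference reasonable, but it remains an inference. The number with scans is not given.
- *That nobody will record who was navigated.* No passage says so.

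**Conclusion.** The point holds as a mismatch between claim and design. Of the three planned comparisons, none varies the site, and a site contrast has 0 degrees of freedom. A conclusion that the targeting method is effective, as against another placement, would not follow from any result of this trial. Feasibility and uncontrolled within-person change at the target remain legitimate conclusions.

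This rests on two assumptions: that Primary Analyses lists every kind of comparison intended, and that no second-site condition is described in material not reproduced here. The second is well supported, because the tACS text ties its montage to the tDCS one whatever the missing figure shows. If neuronavigation did shift placement for some participants, that would be incidental variation and not a planned comparison of sites.

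The relation between the scans and the named positions is a lesser matter. The protocol leaves it open, and on its own it would be only missing detail.

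**What to change.** In the Design and Statistical Methodology rows of the synopsis, replace the aim of testing or determining the effectiveness of the targeting methodology with wording such as:

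> *To assess feasibility, and to describe within-person change in SSVEP, PANSS and biological motion, during stimulation at one site derived from lesion-network mapping. Site specificity is not tested. The comparison of tDCS with tACS is a comparison of waveforms at the same site.*

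Leave the Study Rationale as it is. Separately, the sponsor should reconcile the statement in Screening and Baseline Procedures about using earlier scans for neuronavigation with the positions named under tACS Montage, saying how the two relate. The choice of placement method is the sponsor's, and nothing here argues for one over another.

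The cost is a few sentences, with no new condition, participants or scans. The downside is a narrower claim: the trial would no longer offer evidence that the targeting method itself works, which its data could not supply in any case.

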**EEG Tasks Directions:**

**IAPS**

*For the next 12 minutes you will be presented with a series of 1-second photographs, which will show pleasant, unpleasant and neutral scenes. Some of the pictures may make you feel uncomfortable so if at any point you want to stop please let me know. There will be a red dot at the center of each picture, so try to keep your eyes centered on that.*

**Visual Steady State**

*For this last task, you will see a series of flashing red/white squares and black/white squares on the screen that will look like a strobe effect. They will appear in the center, left, right or both sides of the screen but please try to keep your eyes focused on the plus sign in the center of the screen. Every time you see the red/white squares, press the number 1 and you won't press anything when you see the black and white squares. This will last for 16 minutes with a break in between.*

**IAPS Survey**

*This is a survey about the pictures that you saw earlier and we want you rate each picture on 2 scales. The first scale is pleasantness, 1 is happy and 9 is unhappy and the second scale is arousal, 1 is stimulated and 9 is bored. There are 60 pictures and please use your best judgment. Do you have any questions?*

## **Visual Assessments**

Three visual assessments will be undergone for all participants: visual working memory, biological motion and speed discrimination. These tests are run via **MATLAB and Eclipse IPE**, respectively

### **Set-Up:**

1. Connect Mac Mini to eye-tracking computer
  - a. Black thick wire (*taped and marked “TDCS”*) with Mac adaptor
2. Move the head and chin rest to be **75 cm from the monitor** (*marked with tape on the floor*)
3. Attach keyboard to computer and place on desk
4. Use alcohol wipe to clean:
  - a. Forehead and chin rest
  - b. Keyboard
5. Open up **“Visual Assessment Instructions”** PowerPoint
  - a. You will use this to describe the tasks to the participant
6. Open up **“Eclipse IPE”**
  - a. Load in **“speedDiscriminationnoClut.java”** and **“oddOneOut.java”**
7. Open up **“MATLAB”**
  - a. Load in **“walker\_nonoise\_task.m”** and **“biomotionwalkerwithnoise.m”**

## **DATABASE Quality Assurance and Analysis**

The clinical database will be reviewed and checked for omissions, apparent errors, and values requiring further clarification using computerized and manual procedures.

### **Description of Study Endpoints**

#### **Primary Endpoint**

Change from baseline in Positive and Negative Syndrome Scale (PANSS) total score after 1 week of tES. Change from baseline in SSVEP voltage after 1 week of tES. Change from baseline in Biological Motion task total score after 1 week of tES.

### **General Statistical Considerations**

All collected study data will be collected on Redcap and processed using R and Matlab software. Descriptive statistics (n, mean, standard deviation, median, minimum and maximum) will be calculated by treatment group for continuous variables.

### **Primary Analyses**

Primary Analysis of the primary, secondary, and additional efficacy endpoints:

Mixed Model Repeated Measures analysis (MMRM)/non- parametric methods will be used to compare using within group differences as well as to determine the difference between the two treatment groups on the primary endpoint depending on the distribution of the data.

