### **Study Visits and Details:**

Participants will complete baseline clinical, neuropsychological, visuoperceptual and neurophysiological assessments (day 0), short-term follow-up (day 5) and long-term follow-up (month 1).

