## **OBJECTIVES**

### **Primary Objective**

The primary objective of this study is to evaluate the effectiveness of tES (cathodal tDCS and 2hz tACS) improving the positive symptoms and negative symptoms associated with psychosis along with electrophysiology outcomes and motion perception.

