## **Clinical Assessments**

### **Positive and Negative Symptom Scale (PANSS)**

The ratings are based on a clinical interview, conducted by trained clinical staff, covering all of the items in the rating scale.

- This rating scale is meant to capture many different types of symptoms including positive, negative and general psychopathology symptoms. The ratings are based on a clinical interview with the participant.
- All items are completed for the past week.
- **Always use the manual** with anchor points when scoring and do not try to score from your memory of the anchor points or by their headings (mild, moderate or severe).

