### **Global Assessment Functioning (GAF)**

Consider psychological, social, and occupational functioning on a hypothetical continuum of mental health-illness. Do not include impairment in functioning due to physical (or environmental) limitations.

Indicate appropriate code for the **LOWEST level of functioning during the week of POOREST functioning in past month**. (Use intermediate level when appropriate, i.e., 45, 68, 72).

[figure not shown]

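### With tDCS always first and tACS always second, the planned tDCS-versus-tACS comparison cannot be separated from period, practice or carry-over

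*Protocol*

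**What the plan says.** The synopsis of the protocol (Design) calls the trial "Open Label, Non-randomized, Crossover Design with Baseline, Day 5 and 1 Month follow up visits" and gives the order: "Participants first entered the cathodal tDCS condition first and then after a washout period (~2 weeks) entered the 2hz tACS condition". Enrollment is 10. The protocol describes no reverse sequence, sham or parallel group.

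Under Primary Analyses, an MMRM or non-parametric methods are to be used for within-group differences and also "to determine the difference between the two treatment groups on the primary endpoint depending on the distribution of the data". The synopsis (Statistical Methodology) announces "Within and Between comparisons to statistical detect differences in symptoms, visual tasks and electrophysiology measures before and after treatment conditions". That sentence is looser, so the Primary Analyses section is the firm evidence of a planned tDCS-versus-tACS comparison.

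The Primary Objective is to "evaluate the effectiveness of tES (cathodal tDCS and 2hz tACS) improving the positive symptoms and negative symptoms associated with psychosis", together with electrophysiology and motion perception. The Primary Endpoint section defines changes from baseline in PANSS total, SSVEP voltage and Biological Motion score. No stated objective compares the two waveforms. Nowhere does the protocol assume that period or carry-over effects are absent.

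**The concern.** In a crossover, the conditions can be compared because some people take them in one order and some in the other. Here everyone takes the same order, so being in the tACS condition and being in the second period are the same fact.

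Order effects are plausible for these endpoints. Biological Motion is a performance task done repeatedly. PANSS is rated by interview in an open-label trial. Practice gain, regression to the mean and expectation can all differ between a first and a second week of stimulation, and an effect of tDCS may persist.

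If the plan is followed, a difference on a primary endpoint could be read as a difference between waveforms when the design cannot tell it from an order effect. The bias can also run the other way and hide a real difference.

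**Working it through.** The protocol gives no alpha, SD or effect size behind its 10 participants, so there is no stated figure to reproduce. The check has an algebraic part, which carries the finding, and an illustration on assumed inputs.

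**1. What the paired difference estimates.** Let τ be the tACS-minus-tDCS effect, π the difference in change between period 2 and period 1, and λ the carry-over from tDCS into period 2. Each person's difference in change, tACS minus tDCS, has expectation τ + π + λ. Only the sum is observed.

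**2. Rank of the model.** Inputs: 10 participants and two periods (synopsis), and three assessment visits, Baseline, Day 5 and 1-Month (Study Timeline). The visits are assumed to be repeated in each period, which the protocol does not say.

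| Mean model | Columns | Rank, fixed order | Rank, 5/5 order |
|---|---|---|---|
| Change scores: subject + condition | 10 + 1 = 11 | 11 | 11 |
| the same + period | 12 | 11 | 12 |
| the same + period + tDCS carry-over | 13 | 11 | 12 |
| Baseline and Day 5: subject, visit, condition, condition × visit, period, period × visit | 10 + 1 + 1 + 1 + 1 + 1 = 15 | 13 | 15 |
| The same terms with three visits | 10 + 2 + 1 + 2 + 1 + 2 = 18 | 15 | 18 |

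Under the fixed order each period column duplicates a condition column, and the condition-by-Day-5 term is not estimable. The contrast can be computed only by leaving period out, that is, by assuming π = λ = 0.

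**3. Illustration.** Assumed: two-sided 0.05, τ = 0, and a total order shift d (π + λ) in units of the SD of the paired difference. For a paired t test with n = 10, the critical value is 2.262 on 9 df and the noncentrality is d√10.

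| d | Noncentrality | False positives, paired t | False positives, exact Wilcoxon signed-rank (simulated) |
|---|---|---|---|
| 0 | 0 | 0.050 | 0.049 |
| 0.25 | 0.79 | 0.109 | 0.105 |
| 0.5 | 1.58 | 0.293 | 0.282 |
| 0.75 | 2.37 | 0.562 | 0.543 |
| 1.0 | 3.16 | 0.803 | not run |

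The non-parametric option gives no protection.

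**4. What a 5/5 order would do.** The period-2-minus-period-1 difference has expectation τ + π + λ₁ in one sequence and −τ + π + λ₂ in the other. Half the difference between sequences is τ + (λ₁ − λ₂)/2, so a common period effect cancels and unequal carry-over does not. The standard error is ½·SD·√(1/5 + 1/5) = SD/√10, the same as for the paired analysis, on 8 df instead of 9. The difference detectable with 80% power moves from 0.996 to 1.012 SD. Simulated false-positive rates at shifts of 0.25, 0.5 and 0.75 SD are 0.050, 0.049 and 0.051.

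**5. Washout timing (minor).** The synopsis does not say whether the washout of about 2 weeks starts after Day 5 or after the 1-month visit. Assume tDCS on days 1–5, 14 washout days, a 1-month visit near day 31 and a 30-day look-back for GAF, which rates the "LOWEST level of functioning during the week of POOREST functioning in past month".
- Washout from Day 5: tACS falls on days 20–24 and the tDCS 1-month visit comes after it. The GAF look-back from day 20 or 24 starts at day −10 or −6 and covers the tDCS days.
- Washout from the 1-month visit: tACS falls on days 46–50. The GAF look-back starts at day 16 or 20 and does not cover them.

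**The case against.** The strongest reply is that the contrast is peripheral. The title says feasibility, the fixed order is disclosed, the objective and all three primary endpoints concern change from baseline, and Primary Analyses names the within-group comparison first. This limits the reach of the finding: within-condition change survives. It does not rescue the contrast, which is still planned on the primary endpoint without a caveat.

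A second reply is that the washout and a fresh baseline deal with order. A washout may reduce carry-over but does nothing for period or practice. A baseline repeated before tACS would cancel a constant shift in level, and then d in the illustration means only a difference in change between periods. That point stands, and the protocol does not say whether the baseline is renewed. A smaller practice gain, regression to the mean or altered expectation in the second week would remain.

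A third reply is that the illustrated error rates rest on shifts found nowhere in the protocol. That is correct. They show scale only, and the rank result does not need them. Nor does confounding make order as likely an explanation as waveform; it means that the data cannot decide between them.

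An analysis plan that is not shown could relabel the contrast, but it could not supply the missing reverse sequence.

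**Conclusion.** The concern holds. The comparison of tDCS with tACS planned under Primary Analyses is not identifiable apart from order: rank 11 of 12 for change scores and 15 of 18 for the three-visit model, against full rank with two sequences. This rests on the single sequence in the synopsis and on no assumed effect size. The false-positive rates of about 11%, 29% and 56% are conditional on the assumed shifts and a two-sided 0.05 level.

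The defect is confined to the between-condition contrast. The before-after change in each condition can be estimated, but it is uncontrolled, and the tACS change always follows tDCS. The washout and GAF point is secondary and arises only if the washout runs from Day 5.

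**What to change.** The synopsis describes the order in the past tense, although other sections say what will be done, so the remedy depends on whether the sequence has been carried out.

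**If it has:**
- Remove the inferential between-condition test from Primary Analyses and from Statistical Methodology in the synopsis.
- Report within-person change from each period's own baseline, and say whether that baseline was renewed before tACS.
- Give tACS minus tDCS as a mean and SD without a p-value, labelled descriptive and confounded with order.
- State that neither waveform can be concluded better than the other.

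This costs no patients or visits. It is a change to a planned analysis, so it should be dated and justified. What is given up is a comparative claim the design cannot support.

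**If the order is still open:** randomise it 5/5 and include a period term. The cost is a 10-person order list and one degree of freedom (detectable difference 1.00 to 1.01 SD). Unequal carry-over would remain inseparable.

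**In either case:** state when the washout starts, reconcile the synopsis with Study Visits and Details and with the GAF look-back, and call the two arms treatment conditions instead of groups, since the same people receive both.
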